#### 10.5.6. Populations for Exploratory Analyses

Populations for exploratory analyses will be described in the SAP.

# 10.6. Demographics, Baseline Characteristics, and Other Background Information

#### **10.6.1.** Demographics and Baseline Characteristics

Demographic and baseline characteristics will be listed and summarized overall, by the two categories of disease severity, and by region (North America and Europe).

#### 10.6.2. Prior and Concomitant Medications

All prior and concomitant medications will be listed and summarized by anatomical therapeutic chemical classification levels 2 and 4. The number and percentage of subjects who are on drugs that could affect behavior and cognition will be summarized.

#### 10.6.3. Subject Disposition

The number and percentage of study subjects who discontinue will be reported overall and by reason for discontinuation.

#### 10.6.4. Study Drug Compliance

Study drug compliance will be listed.

Confidential Page 92 of 115

# 10.7. Efficacy Analyses

#### 10.7.1. Hierarchical Hypothesis Testing

A fixed sequence hierarchical testing approach will be used to test multiple endpoints in a predefined order to control the family-wise type 1 errors arising from multiple comparisons. Only after a success on the testing of the previous endpoint will the next endpoint be tested.

If the primary endpoint is significant at the 0.05 significance level, the key secondary endpoints will be analyzed using a fixed-sequence step-down procedure to control for multiplicity in the secondary endpoints. The three key secondary endpoints (CBL to week 78 in A-IADL, CDR and DAD) will be tested in sequential order at significance levels of 0.05. The order of testing will be A-IADL, followed by CDR-SB, followed by DAD [Figure 9]. The hypothesis testing for the additional clinical endpoints will be considered exploratory.

The order of the hierarchical tests is:

- 1. Primary efficacy endpoint: CBL to Week 78 in ADAS-Cog 13
- 2. Key secondary endpoint: CBL to Week 78 in A-IADL
- 3. Key secondary endpoint: CBL to Week 78 in CDR-SB
- 4. Key secondary endpoint: CBL to Week 78 in DAD

Confidential Page 93 of 115

[figure not shown]

Figure 9 Hierarchical Testing Process in Study ALZ-801-AD301

ADAS-Cog 13: 13-item Alzheimer's Disease Assessment Scale – cognitive subscale; A-IADL: Amsterdam Instrumental Activities of Daily Living; CDR-SB: Clinical Dementia Rating – Sum of Boxes; DAD: Disability Assessment for Dementia

#### 10.7.2. Primary Efficacy Analysis

Unless otherwise specified, all primary efficacy analyses will be performed using the mITT population. Analyses of the primary endpoint of ADAS-Cog 13 will be performed with a likelihood based linear MMRM on treatment observed case (OC) data. The OC data set will consist of actual observations recorded at each visit during the double-blind treatment period and no missing data will be imputed. The model terms will include treatment, the stratification factors of use of concomitant AD medications (AChEI or none), age group (50 through 65 years or > 65 at the Screening – Part 1 Visit), gender, disease severity based on MMSE at the Baseline Visit, baseline ADAS-Cog 13 values, visit (VISIT), and treatment by visit interaction. The visit variable will be used to define the within-subject repeated measures over time. The least squares mean (LSM) for each treatment at each visit will be generated together with its 95% confidence interval, and the LSM difference between the active treatment and placebo will also be calculated; together

Confidential Page 94 of 115

with its standard error, and the 2-sided 95% confidence interval. For the primary endpoint at 78 weeks, treatment comparisons will be done at the 0.05 significance level.

All data collected during the study will be used in the statistical analysis. Additional details will be described in the final SAP. Sensitivity testing of the primary endpoint will include MMRM analyses for the PPP, and the CP.

For subjects who discontinue treatment prior to trial completion, every attempt will be made to have them continue with clinic visits and study assessments. Particular attention will be given to collecting Week 78 ADAS-Cog 13 assessments, regardless of when subjects discontinued treatment. These data from retrieved dropouts data will be used to impute missing data using multiple imputation method as a sensitivity analysis for the primary endpoint. This method assumes that the best reflection of what happened to the early dropout patients at Week 78 are the retrieved dropouts. For those subjects who terminate treatment prematurely but have Week 78 assessments, and the intermediate missing off-treatment data will be imputed by interpolation for analyses.

### 10.7.3. Secondary Endpoint Analyses

The same MMRM method applied to the primary efficacy endpoint will be used to evaluate the between-treatment difference for the key secondary endpoints. No explicit missing data imputation will be performed except for that which is inherent in the MMRM. Differences between treatments, the p-values, and the 2-sided 95% CIs will be calculated within the framework of MMRM.

Note that only the post-baseline visits on which the endpoints are scheduled to be measured will be included in the model. The secondary endpoint analyses will be analyzed using the mITT population, PPP, and CP.

All other secondary efficacy endpoints will be analyzed using either MMRM, analysis of covariance (ANCOVA), or nonparametric inferential statistical methods and will be described in the SAP.

#### 10.7.4. Subgroup Analyses

Efficacy analyses in the sub-groups of subjects with baseline MMSE  $\leq$  26 or > 26 may be performed using the MMRM method.

It is expected that approximately 80% of all subjects would be on stable doses of AChEI, approximately 90% in Mild AD and 70% in MCI. It is expected that the use of AChEI will be similar between the ALZ-801 and placebo arms. Subgroup analysis of efficacy by use of AChEI will be performed.

### 10.8. Biomarker Analyses

#### 10.8.1. Cerebrospinal Fluid Biomarker Analyses

Serial CSF samples from the baseline, Week 52 and Week 78 visits will be stored and batched for analyses. Samples from multiple subjects and study sites will be analyzed in batches, at a single central laboratory, using standardized procedures and validated assays, or well performing, widely accepted CSF assays if not validated.

Confidential Page 95 of 115

The CSF biomarker analyses will be performed on subjects (CSF sub-study) who have a baseline and at least one post-baseline CSF biomarker sample. The change from baseline and percent change from baseline in CSF biomarkers will be summarized by visit and treatment group. The between groups comparisons of change from baseline in each CSF biomarker will be analyzed using an MMRM model with treatment, the use of concomitant AD medications (AChEI or none), age group (50 through 65 years or > 65 years from the result of the Screening – Part 1 Visit), gender, disease severity based on MMSE at the Baseline Visit, baseline CSF biomarker level, visit, and treatment by visit interaction in the model.

#### 10.8.2. Plasma Biomarker Analyses

Serial plasma samples from screening and each subsequent visit will be stored and batched, under GLP conditions, for analyses. Samples from multiple subjects and study sites will be analyzed at a single central laboratory using validated assays, or well performing, widely accepted plasma assays if not validated.

The plasma biomarker analyses will be performed on subjects who have a baseline and at least one post-baseline biomarker sample. The change from baseline and percent change from baseline in plasma biomarkers will be summarized by visit and treatment group. The change from baseline in each plasma biomarker will be analyzed using an MMRM model. The model will include treatment, the use of concomitant AD medications (AChEI or none), age group (50 through 65 years or > 65 years at the Screening – Part 1 Visit), gender, disease severity based on MMSE at the Baseline Visit, baseline plasma biomarker level, visit, and treatment by visit interaction in the model.

#### 10.8.3. Imaging Biomarker Analyses

Analysis of hippocampal volume and cortical thickness will be performed using the same MMRM approach described for analysis of the primary clinical endpoint. The MMRM model will include treatment, the use of concomitant AD medications (AChEI or none), age group (50 through 65 years or > 65 years at the Screening – Part 1 Visit), gender, disease severity based on MMSE at the Baseline Visit, baseline plasma biomarker level, visit, and treatment by visit interaction. The MRI magnet strength (1.5 or 3 Tesla) will also be included as a covariate in the model.

The imaging biomarker analyses will be performed on the subjects who have a baseline and at least one post-baseline vMRI assessment.

# **10.9.** Tests of Cognition and Function

Tests of cognition and function will be evaluated using the same approach described for the analysis of the fluid biomarkers.

# **10.10.** Safety Analyses

Continuous safety data will be analyzed descriptively with summary statistics; and categorical safety data will be summarized using counts and percentages. The safety assessments will also include analyses of MRI findings (ARIA-E and ARIA-H) based on the central readings.

Confidential Page 96 of 115

#### 10.10.1. Adverse Events

For data summarization, AEs will be classified into standard terminology using the Medical Dictionary for Regulatory Activities (MedDRA), and reported by system organ class and preferred term.

TEAEs are defined as AEs that either started or worsened after administration of the first dose of study drug.

The number and percentage of the following types of AEs will be reported:

- TEAEs;
- TEAEs that led to study discontinuation;
- TEAEs related to study drug;
- TEAEs by maximum severity;
- SAEs; and
- SAEs related to study drug.

A listing of AEs will also be compiled.

#### 10.10.2. Clinical Laboratory Evaluations

Clinical laboratory test results will be summarized and listed. Summary statistics for the CBL and the percentage out of range (normal reference range as established by the central laboratory) will be presented for each post-baseline time point.

Clinically notable changes in LFTs will be summarized and listed for individual study subjects. The criteria for clinically significant LFT results are as follows:

- ALT  $> 5 \times ULN$ ,
- AST  $> 5 \times ULN$ , or
- TBL  $> 3 \times ULN$

#### 10.10.3. MRI Safety Evaluations

The Screening – Part 2, Week 26, Week 52, and Week 78 MRIs will be assessed for occurrence of ARIA-E, ARIA-H, and macrohemorrhage by the central imaging provider (Bioclinica). Listings of these findings will be provided and summarized using descriptive statistics.

#### **10.10.4.** Vital Signs

Changes from baseline in vital sign measurements will be summarized.

Clinically notable systolic and diastolic BP while sitting will be listed for individual study subjects and summarized using descriptive statistics. Clinically notable criteria are indicated in [Table 4].

Confidential Page 97 of 115

	·	6
Parameter	High Threshold	Low Threshold
Systolic BP	> 30 mm Hg increase from baseline	> 30 mm Hg decrease from baseline
Diastolic BP	> 20 mm Hg increase from baseline	> 20 mm Hg decrease from baseline
Pulse rate	> 120 beats/min and an increase in pulse rate of ≥ 15 beats/min from baseline	< 40 beats/min and a decrease in pulse rate of ≥ 15 beats/min from baseline
Body temperature	> 39.0°C (≥ 102.2°F)	< 35.0°C (≤ 95.0°F)

Table 4 Criteria for Clinically Notable Vital Sign Abnormalities

BP: blood pressure

#### 10.10.5. Electrocardiograms

All ECG intervals and durations will be reviewed for notable abnormalities according to the criteria in [Table 5]. Clinically notable abnormalities and ECG findings considered to be clinically significant will be listed. The number and percentage of study subjects who have a clinically notable ECG interval abnormality or other clinically significant ECG finding will be summarized. Assessment of clinically notable abnormalities will be based on the average of triplicate ECG readings. The criteria for QTcF are based on the upper threshold in elderly subjects [Reardon & Malik, 1996], and from other recent AD studies.

Table 5 Criteria for Clinically Notable Electrocardiogram Interval Abnormalities

Interval/Duration	High Threshold	Low Threshold
PR interval	PR interval ≥ 220 msec	PR interval ≤ 120 msec
QRS duration	QRS duration $\geq$ 120 msec and an increase in QRS duration of $\geq$ 20 msec from baseline	_
QT interval	QT interval > 500 msec	_
QTcF interval	QTcF interval $> 500$ msec and an increase in QTcF interval of $\ge 60$ msec from baseline	-

QRS duration: interval from the beginning of the Q wave to the termination of the S wave, representing the time for ventricular depolarization; QT interval: interval representing the time for both ventricular depolarization and repolarization to occur; QTcF: corrected QT interval using Fridericia's correction; PR interval: time from the onset of the P wave to the start of the QRS complex.

#### 10.10.6. Physical Examination

The number and percentage of subjects with abnormal physical examination findings will be summarized. Analyses of subjects with weight loss of > 6% from baseline will be provided for subjects with weight loss without intentional dieting.

#### 10.10.7. Neurological Examination

The number and percentage of subjects with abnormal neurological examination findings will be summarized.

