## Safety and Tolerability

- Incidence and nature of TEAEs, serious TEAEs, and TEAEs leading to withdrawal
- CBL in vital signs and physical exam, including body weight
- CBL in laboratory parameters (clinical chemistry, hematology, coagulation tests)
- CBL in 12-lead ECG parameters
- CBL in MRI central readings for ARIA-E or ARIA-H
- CBL in the C-SSRS

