8.5.5 Evaluation of Electrocardiogram (ECG) Findings

Electrocardiogram (ECG) Findings

Electrocardiograms will be assessed by a central reader and will be recorded at the following visits:

- Screening/Visit 1
- Visit 4/Day 43
- Visit 5/Day 92

- Visit 7/Week 26
- Visit 9/Week 52
- Visit 11/Week 78

The following quantitative parameters will be reported by the central reader: heart rate, PR interval, QRS duration, QT interval (uncorrected), and QT interval with Fridericia's correction (QTcF). Change from baseline and percent change from baseline by visits will be calculated for each parameter. The number and percent of patients within each category (normal, abnormal not clinically significant, and abnormal clinically significant) will also be summarized by visit. A standard triplicate 12-lead ECG will be performed at the Screening, Visit 4 and Visit 5. At subsequent visits, a single 12-lead ECG will be performed unless there is evidence of QT prolongation, in which case a triplicate ECG must be performed. Assessment of clinically notable abnormalities will be based on the average of triplicate ECG readings. To be conservative, the worst interpretation of the three readings will be used to generate the summary of ECG clinically notable abnormalities table. The denominator for the percentages will be the number of patients with a result at the specific visits for each parameter.

Clinically notable changes in ECGs will be listed for individual study subjects and tabular summaries provided per visit. The criteria for clinically significant ECGs results are as follows:

- PR interval \geq 220 msec
- PR interval ≤ 120 msec
- QRS duration ≥ 120 msec and increase of ≥ 20 msec from baseline
- OT interval >500 msec
- QTcF interval > 500 msec and increase of ≥ 60 msec from baseline

Categorical Analyses of QTcF Interval

At each visit with ECG, observed QTcF data will be summarized into the following categories and shift tables provided:

- Categories of QTcF \leq 450msec, 451-480 msec, 481-500 msec, and \geq 500 msec
- Categories of QTcF > 450 msec, > 480 msec, and > 500 msec
- Categories of CBL in QTcF: ≤ 10 msec, 11-30 msec, 31-60 msec
- Categories of CBL in QTcF: > 30 msec, > 60 msec

Vital Signs

Vital signs will be assessed at all visits except Visit 3 and Visit 6. The following parameters will be summarized: systolic blood pressure (SBP), diastolic blood pressure (DBP), body

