temperature and respiratory rate. Weight and Height will also be summarized for available visits. These parameters will be summarized through change from baseline and percent change from baseline in similar fashion as the ECG parameters.

Vital signs will be assessed through potentially clinically significant (PCS) criteria. Patients will be counted if they meet the criteria at any time post-baseline. The denominator for the percentages will be the number of patients with a result at the specific visits for each parameter.

Clinically notable systolic and diastolic BP will be listed for individual subjects and summarized using descriptive statistics. Clinically notable criteria are described in Table 17.

 Table 17 Criteria for Clinically Notable Vital Sign Abnormalities

Parameter	High Threshold	Low Threshold
Systolic BP	> 30 mm Hg increase from baseline	> 30 mm Hg decrease from baseline
Diastolic BP	> 20 mm Hg increase from baseline	> 20 mm Hg decrease from baseline
Pulse rate	> 120 beats/min and an increase in pulse rate of ≥ 15 beats/min from baseline	< 40 beats/min and a decrease in pulse rate of \geq 15 beats/min from baseline
Body	> 39.0°C (≥ 102.2°F)	< 35.0°C (≤ 95.0°F)
temperature		

BP: blood pressure

Physical Examinations

Physical examinations will be performed at all visits except Visit 3 and Visit 6. All data will be listed. The number and percentage of subjects with abnormal neurological examination findings will be summarized.

Neurological Examinations

Neurological exam will be performed at the following visits:

- Screening/Visit 1
- Visit 7/Week 26
- Visit 9/Week 52
- Visit 11/Week 78
- Safety Follow up Visit/Week 82

All data will be listed. The number and percentage of subjects with abnormal neurological examination findings will be summarized.

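### Examination and PR/QT summaries do not separate new abnormalities from those present before dosing, and the SAP specifies no physical-examination table

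*Protocol*

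**What the plan says.** **Endpoint.** Protocol 4.2.1, Safety and Tolerability, lists "CBL in vital signs and physical exam, including body weight".

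**Examination analyses in the Protocol.** Section 10.10.6 reads "The number and percentage of subjects with abnormal physical examination findings will be summarized", followed by an analysis of weight loss. Section 10.10.7 does the same for the neurological examination: "The number and percentage of subjects with abnormal neurological examination findings". Neither is limited to findings after dosing, or to findings that are new or worse, and neither mentions a shift table.

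**Examination analyses in the SAP.** Both examinations are covered under SAP 8.5.5. The paragraph headed Physical Examinations plans a listing and then this summary: "The number and percentage of subjects with abnormal neurological examination findings will be summarized". The identical sentence closes the Neurological Examinations paragraph. That paragraph introduces its visit list with "Neurological exam will be performed at the following visits", and the list begins with Screening.

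**ECG criteria.** Protocol 10.10.5 (Table 5) and SAP 8.5.5 share the same limits. For PR they are "PR interval ≥ 220 msec" and "PR interval ≤ 120 msec", and for QT the limit is above 500 msec. None of these refers to baseline. The QRS row does: "QRS duration ≥ 120 msec and increase of ≥ 20 msec from baseline". The QTcF row likewise requires an increase of at least 60 msec.

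**Baseline.** SAP 8.1.3 defines baseline for all safety measures as the last available pre-dose value. The Schedule of Assessments places a physical examination at Screening Part 2 and at the Baseline Visit, and a neurological examination and an ECG at Screening Part 2.

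**The concern.** An endpoint defined as a change from baseline needs an analysis that uses the baseline. Body weight has one (Protocol 10.10.6, SAP 8.5.4). Examination findings do not, although the pre-dose examinations are collected and the SAP defines which value is the baseline. In the SAP the physical examination has, on its wording, only a listing.

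Subjects are 50 to 80 years old, and the neurological examination covers gait, reflexes, sensation and speech (Protocol 7.1.10.3). Some will probably have a long-standing finding at entry. If such subjects are counted in both arms, they add the same number of non-informative cases to each arm and pull the arms together. A finding that worsens from an abnormal baseline does not show at all in a yes/no count.

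The ECG table has the same weakness in two rows. Exclusion criterion 10 removes clinically significant ECG findings and sets QTcF limits, but gives no PR limit. A subject with a stable PR of 220 msec or more, judged not clinically significant, may enter and be notable at every later ECG visit.

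**Working it through.** The plan gives no figure of its own on this point, so there is none to reproduce. The check compares the texts and then shows how much contrast could be lost.

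**1. Which outputs refer to baseline?**
- Laboratory values: shift tables (SAP 8.5.3).
- ARIA, white-matter and ischaemic MRI findings: shift tables (SAP 8.5.3).
- QTcF categories: shift tables (SAP 8.5.5).
- QRS and QTcF notable values: limit plus increase from baseline.
- PR and QT notable values: limit only.
- Neurological examination: number and percentage abnormal only.
- Physical examination: number and percentage abnormal in the Protocol, listing only in the SAP.

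**2. Dilution formula.** Let b be the proportion abnormal before dosing and remaining so, and q the new-onset rate among the others. Counting everyone with an abnormality gives

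p = b + (1−b)q

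The difference between arms is then (1−b)(q₁−q₀), and the ratio is [b + (1−b)q₁] / [b + (1−b)q₀], which moves toward 1 as b rises.

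**3. Illustration.** The values of b, q₀ (placebo) and q₁ (active) are assumptions, because the documents give none of them.

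| q₀ vs q₁ | b | All abnormal, placebo vs active | Difference (points) | Ratio | Ratio, new-onset only |
|---|---|---|---|---|---|
| 5% vs 15% | 0% | 5.0% vs 15.0% | 10.0 | 3.00 | 3.00 |
| 5% vs 15% | 10% | 14.5% vs 23.5% | 9.0 | 1.62 | 3.00 |
| 5% vs 15% | 30% | 33.5% vs 40.5% | 7.0 | 1.21 | 3.00 |
| 5% vs 15% | 50% | 52.5% vs 57.5% | 5.0 | 1.10 | 3.00 |
| 5% vs 10% | 10% | 14.5% vs 19.0% | 4.5 | 1.31 | 2.00 |
| 5% vs 10% | 30% | 33.5% vs 37.0% | 3.5 | 1.10 | 2.00 |

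Example, b = 30%: 0.30 + 0.70×0.05 = 0.335 and 0.30 + 0.70×0.15 = 0.405. The difference is 0.70×0.10 = 0.07.

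As a gauge of lost contrast only, take a two-sided 0.05 comparison of two proportions at the Protocol's 150 per arm with 5% vs 15%. Counting all abnormal subjects gives power of 51% at b = 10% and 24% at b = 30%. Counting new onset among subjects normal at baseline (135 and 105 per arm) gives 79% and 68%.

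**4. PR.** Assume onset of 1% vs 4%, a true ratio of 4. With 3% already outside the limit, the rates are 1−0.97×0.99 = 3.97% and 1−0.97×0.96 = 6.88%, ratio 1.73. With 10%, they are 10.9% and 13.6%, ratio 1.25.

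**5. QT.** This gap is narrower, because entry requires QTcF of at most 450 msec (men) or 470 msec (women). With QTcF = QT/RR^(1/3), a pre-dose QT above 500 msec needs RR above (500/450)³ = 1.37 s in men, a rate below 60/1.37 ≈ 44 beats/min. In women it needs RR above (500/470)³ = 1.20 s, a rate below about 50 beats/min.

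**The case against.** The strongest reply has four parts.

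- **The text is silent, not wrong.** A reader might infer that the plan instructs analysts to count pre-existing abnormalities as on-treatment findings. The documents do not say so. The sentences are one-line descriptions, and a neurological table by visit would show the Screening rate beside the later ones. This stands: the defect is an omission that permits such counting. Marginal rates by visit would still not show which subjects changed.
- **The endpoint is partly met.** Protocol 8.1 also lists the occurrence of abnormal physical findings as a safety endpoint, and Protocol 10.10.6 delivers that. Weight is analysed from baseline. The neurological examination is not in the change-from-baseline endpoint, and PR belongs to the separate ECG endpoint. All of this stands, but none of it supplies the missing change analysis for the physical examination.
- **Other outputs catch new findings.** A reader might infer that no other table helps, and that would be too strong. New clinically significant examination abnormalities are adverse events (Protocol 8.1.1), deterioration of a condition present at screening is recorded as one (8.3), and new or worsened events are tabulated by arm (SAP 8.5.2). SAP 8.5.5 also plans change from baseline by visit for each ECG parameter, PR and QT included, and a normal/abnormal grading by visit. This mitigates the problem. It leaves out new examination signs not judged clinically significant, and it does not change the PR and QT threshold counts.
- **The size is assumed.** A reader might infer that a real drug signal would be swamped. The documents give neither baseline prevalence nor onset rates, safety data are descriptive (Protocol 10.10), and the risk difference falls less steeply than the ratio. This stands.

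**Conclusion.** The point holds as a gap in specification. No change-from-baseline analysis of examination findings is planned although the Protocol names one for the physical examination. The SAP specifies no physical-examination table, apparently because the neurological sentence was repeated in its place. The PR and QT threshold counts lack the baseline condition applied to QRS and QTcF.

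The direction of the effect is certain if abnormal subjects at baseline are counted and remain abnormal: the risk difference is multiplied by (1−b). The size is not known. It is nil at b = 0 and, under the assumed rates above, takes a risk ratio of 3.00 to 1.62 at b = 10% and 1.21 at b = 30%. For PR only the threshold table is affected, and for QT the entry limits on QTcF make the gap small. No inferential conclusion is at risk, because no safety test is planned. The change is worth making because it costs almost nothing and brings these tables into line with those for laboratory values, MRI and QTcF.

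**What to change.** In SAP 8.5.5, with matching wording in Protocol 10.10.5 to 10.10.7 if the Protocol is amended:

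1. Correct the Physical Examinations paragraph so that it specifies a summary of physical-examination findings.
2. Present the physical and neurological examinations by arm as shifts from baseline to worst post-baseline result. Alternatively, count subjects whose finding is new or worse than at the last pre-dose examination.
3. In the PR and QT threshold table, include in numerator and denominator only subjects who did not meet that limit at baseline.
4. Keep every threshold as it is, and keep pre-existing abnormalities in the listings.

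The cost is SAP wording and table shells. The pre-dose examinations and ECGs are already collected, so no new data are needed.
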